## CONFIDENTIAL

Thereafter, laboratory tests must be repeated weekly during the vaccination phase, up to the Week 6 vaccination. Tests to be repeated prior to the weekly vaccination. Haematology and biochemistry results do not need to be reported and checked before each vaccination is given.

- Haematology: detailed in [Section 7.1.3](#).
- Biochemistry: detailed in [Section 7.1.3](#).
- CEA sample
- Urinalysis: detailed in [Section 7.1.3](#).
- Research sampling (Please see [Section 8.0](#)):
  - **Research bloods:** within one hour prior to the 3rd, 4th and 6th vaccination.

- [REDACTED]

[REDACTED]

[REDACTED]

### 7.3 Evaluations after vaccination

#### 7.3.1 Two weeks post vaccination visit

Two weeks after the patient has received their last vaccination they should be assessed for:

- Adverse events since the last visit. The start and stop dates of the AE together with the relationship of the event to AST-VAC2 (and COVID-19 vaccination if applicable) must be recorded in the medical records. All AEs must be graded according to NCI CTCAE Version 4.02 and protocol specific ISR grading system (See [Section 9.0](#) for further details regarding AE reporting requirements and ISR grading system).
- Concomitant medications (details should be recorded in the medical records).
- Research bloods.
- [REDACTED]

#### 7.3.2 End of Vaccination visit

The End of Vaccination visit should be performed 30 days (+/- 5 days) after the last AST-VAC2 vaccination. The following investigations should be performed wherever possible.

- A symptom-directed physical examination including WHO PS, vital signs (temperature, seated BP and pulse rate), weight
- Haematology: detailed in [Section 7.1.3](#).
- Biochemistry: detailed in [Section 7.1.3](#).
- CEA sample
- Urinalysis: detailed in [Section 7.1.3](#).
- ECG (unless otherwise indicated by the patient's condition)
- Assessment of AEs (all AEs should be collected until this visit; after this visit only information on ongoing and new AST-VAC2-related AEs should be collected; see [Section 9.3](#)) and
- Review of concomitant medications

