## CONFIDENTIAL

If the patient is administered a COVID-19 vaccination during the AST-VAC2 vaccination period, there should be a 48 hours interval between the two vaccinations and they should be administered to different sites. The AST-VAC2 vaccination should be delayed as needed to accommodate this interval.

If the patient is withdrawn from further trial treatment, follow up information and post vaccination research blood [REDACTED] sampling will still be applicable unless the patient withdraws consent from further follow up and participation in the trial or if the Sponsor advises that further sampling is not required.

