### 5.4 Duration of treatment

Treatment should continue so that the patient receives six vaccinations unless (a) the patient asks to be withdrawn, (b) there is evidence of disease progression (as per Immune-Related Response Criteria (irRC) given in [Appendix 3](#)), (c) the patient is experiencing unacceptable toxicity or (d) the investigator feels the patient should stop the vaccinations for any other reason. Other reasons are listed in [Section 11.0](#).

An End of Vaccination visit will be carried out 30 days post the last vaccination day. This visit will document any emerging AEs since the last vaccination. Adverse events present at this visit, attributed to AST-VAC2 (highly probably, probably or possibly related) will be followed up until resolution or stabilisation of these events (even if the patient starts another anti-tumour treatment).

If a patient terminates treatment prematurely, an End of Vaccination visit should be performed within 30 days of the last vaccination day or when the decision is taken to withdraw the patient from further vaccinations or the trial. These patients should also be asked to continue attending hospital for the 3, 6 and 12 month from first vaccination follow-up visits to provide blood samples for immune analysis (unless the patient withdraws consent from further follow up and participation in the trial or if the Sponsor advises that further sampling is not required).

Patients will be asked to attend follow up as per Section 7.4 until the end of trial (EoT) is declared. The 'End of Trial' will be declared when all patients have either withdrawn (see [Section 11.0](#)) from the trial or died, or the last patient has completed their final follow-up visit (5 years post the first vaccination), whichever is the latter.

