### 9.3.3 Eligible patients

For eligible patients, SAE and AE collection and monitoring will commence at the time the patient gives their written consent to participate in the trial by signing the main trial consent form and will continue until 30 days after the last vaccination (administration of IMP). From this time point until the patient withdraws, dies or completes the trial, new or ongoing AST-VAC2-related AEs will be collected (regardless of whether the patient goes on to other anti-cancer therapies).

Should an Investigator become aware of any AST-VAC2 -related SAEs after the patient has completed the protocol-mandated follow-up period (as specified above), these must also be reported to the Sponsor within the expedited timelines in Section 9.4.

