## 11 PATIENT WITHDRAWAL BEFORE COMPLETION OF TREATMENT SCHEDULE

AST-VAC2 has been classified as an ATIMP therefore extended follow up (up to five years post first vaccination) is applicable for all patients who receive the IMP.

The Investigator must make every reasonable effort to keep each patient on trial for the whole duration of the trial in order to collect long term safety and pharmacodynamic data. However, if the Investigator removes a patient from the trial (prior to completion of the vaccinations) or if the patient declines further participation, final assessments (as per the 'End of Vaccination' visit), should be performed ideally before any subsequent therapeutic intervention. All the results of the evaluations and observations, together with a description of the reasons for withdrawal from the trial, must be recorded in the patient's medical records and in the eCRF.

A patient may stop vaccination due to AEs but would not be withdrawn from the trial and would continue for follow-up of safety, survival and tertiary endpoints unless they withdraw.

The following are justifiable reasons for the Investigator to withdraw a patient from the trial.

- Withdrawal of consent.
- Serious deviation from the trial protocol (including persistent patient attendance failure and persistent non-compliance).
- Sponsor's decision to terminate the trial.
- Withdrawal by the Investigator for clinical reasons not related to AST-VAC2.
- Loss to follow up.

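### Protocol 7.3.2 and 9.3.3 give different end points for all-cause AE collection, and the gap can be wide for patients who stop vaccination early

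*Protocol*

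**What the plan says.** Four parts of the protocol bear on when a site stops recording all AEs and starts recording only those judged related.

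- **Section 7.3.2** makes the switch at a visit: "all AEs should be collected until this visit; after this visit only information on ongoing and new AST-VAC2-related AEs should be collected". It then points to Section 9.3. The visit itself is scheduled in the same section: "The End of Vaccination visit should be performed 30 days (+/- 5 days) after the last AST-VAC2 vaccination".
- **Section 9.3.3** makes the switch at a fixed time. For eligible patients, collection of AEs and SAEs starts at main-trial consent and "will continue until 30 days after the last vaccination (administration of IMP"). From then on, "new or ongoing AST-VAC2-related AEs will be collected".
- **Section 5.4** moves the visit for a patient who stops early: "an End of Vaccination visit should be performed within 30 days of the last vaccination day or when the decision is taken to withdraw". No minimum interval after the last dose is given.
- **Section 11** says that the final assessments for a patient leaving before the vaccinations are complete "should be performed ideally before any subsequent therapeutic intervention", which can also bring the visit forward.

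The primary endpoint (Section 3.1.1) is the frequency, causality and severity of each AE, related or not. SAP Section 7.5 (Outcome Measure 1) counts SAEs, non-serious AEs and Grade ≥3 AEs overall, and again for related events. SAP Section 5.7 defines treatment-emergent AEs by onset relative to the first vaccination and gives no end date. SAP Section 7.4 describes safety collection as running to two years from the first dose and does not mention the switch to related-only collection.

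**The concern.** Section 7.3.2 refers the reader to Section 9.3, but 9.3.3 has a different stopping point. Nothing says which governs when the visit is early. For completers the difference is small. For a patient who stops early, the visit can come well before Day 30, and a site working from the visit section could in good faith stop recording events it judges unrelated.

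Those events belong in the all-AE and Grade ≥3 counts of the primary outcome. Progression and unacceptable toxicity are among the reasons for stopping in Section 5.4, so the patients exposed to a shorter window are informative ones, and the trial has at most eight patients. The SAP neither equalises the window nor discloses it, so a reader of the AE tables could not tell over what period unrelated events had been sought.

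**Working it through.** The check is date arithmetic on the protocol's own rules. No sample-size or power figure is involved.

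**Inputs**
- Six vaccinations 7 days apart (Section 5.2): Days 1, 8, 15, 22, 29 and 36 at exact spacing.
- Calendar cut-off: 30 days after the last vaccination (9.3.3).
- Visit cut-off: 30 ± 5 days for completers (7.3.2); up to 30 days, or at the decision to stop, for early stoppers (5.4).
- Two-week visit (7.3.1): "Two weeks after the patient has received their last vaccination they should be assessed for" AEs since the last visit, among other items, with no restriction to related events.
- Delay rule (5.3.2): up to two weeks for certain unresolved related AEs.

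**The plan's own figure.** Under 9.3.3 a completer is covered to Day 36 + 30 = Day 66, and a patient who stops after the second vaccination to Day 8 + 30 = Day 38. Section 7.3.2 reproduces the 30 days only when the visit falls exactly on the 30th day after the last dose.

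**Window under 7.3.2.** Days lost = 30 − w, where w is the time from last dose to the cut-off.

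| Situation | w (days) | Days lost | Share of 30 |
|---|---|---|---|
| Completer, earliest visit (Day 36 + 25 = Day 61) | 25 | 5 | 17% |
| Completer, latest visit (Day 36 + 35 = Day 71) | 35 | none (5 extra) | – |
| Early stopper, decision and visit at next weekly attendance | 7 | 23 | 77% |
| Same patient, if the two-week visit still captures all AEs | 14 | 16 | 53% |
| Early stopper, decision after a full two-week delay (7 + 14) | 21 | 9 | 30% |

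**Illustration of what a shorter window records.** The documents give no rate of unrelated AEs, so the 30-day risk p of a first unrelated AE is assumed at 20%, 50% and 80%, with a constant hazard. The chance of recording one within w days is 1 − (1 − p)^(w/30).

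| Assumed p over 30 days | 7 days | 14 days |
|---|---|---|
| 20% | 5% | 10% |
| 50% | 15% | 28% |
| 80% | 31% | 53% |

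These figures apply only to an early stopper, only to unrelated events after the last dose, and only if the site follows 7.3.2. They are not an estimate of bias in the trial's results.

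**The case against.** The strongest reply is that the matter is largely settled by the cross-reference. Section 7.3.2 sends the site to Section 9.3, where 9.3.3 covers all eligible patients and makes no exception for early stoppers. A site that follows the pointer collects for 30 days. This stands in part: the short window is permitted, not certain. But the pointer leads to a different cut-off without saying that it overrides the sentence that contains it.

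A reader might infer more than the documents support in three ways.

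- *That unrelated SAEs before Day 30 go uncollected and the sponsor never sees them.* Section 9.4 requires all SAEs to be reported regardless of causality, 9.3.3 runs SAE collection to 30 days, and Section 13.4 describes deaths within 30 days of the last vaccination separately. SAEs are therefore probably still reported. What remains is that 9.4 gives no end date, so the point is not closed.
- *That the two-week visit cannot help because it falls after the switch.* Section 7.3.1 does not limit that visit to related events, and no text cancels it for early stoppers. On patients taken off vaccination, Section 5.3.2 begins "If the patient is withdrawn from further trial treatment, follow up information and post vaccination research blood" and keeps follow-up in place unless consent is withdrawn or the sponsor advises that sampling is not needed. The practical minimum may therefore be about 14 days.
- *That patients stopped for toxicity typically have a 7-day window.* On the delay route in 5.3.2 the decision can come at about 21 days or later, and 5.4 does not rule out a visit after Day 30.

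It is also fair to say that the SAP plans no formal or subgroup analysis, so no comparison of completers with early stoppers is damaged. A patient with an earlier AE already counts in the row for at least one event. The event counts and the Grade ≥3 figures are still affected.

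**Conclusion.** The two sections conflict and should be reconciled. The gap is up to 5 days for completers. For early stoppers it can reach 23 of 30 days if the visit takes place at the next weekly attendance, or 16 of 30 if the two-week visit still captures all AEs. The possible loss is confined to AEs judged unrelated, mainly non-serious ones, between the visit and Day 30. Related AEs are collected under both rules.

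The conclusion rests on the visit being held at the decision to stop and on the site reading 7.3.2 literally. The documents do not establish that this will happen, or how many of the at most eight patients would be affected, so a downward bias in the primary endpoint is possible rather than shown. The change is still worth making: the primary endpoint counts every AE, the sample is very small, and the remedy is the sponsor's own 30-day rule.

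**What to change.** - **Protocol 7.3.2:** replace the visit-based cut-off with that of 9.3.3, so that all AEs and SAEs, regardless of causality, are collected until 30 days after the last vaccination, whatever the date of the End of Vaccination visit. A single calendar cut-off also removes the variation of 25 to 35 days among completers.
- **Protocol 5.4:** add that when the visit takes place before Day 30 after the last vaccination, the site makes an AE contact at Day 30. A telephone call is enough; Sections 7.4.1, 7.4.2 and 7.4.4 already accept calls for AE follow-up.
- **SAP 5.7, 7.4 and 7.5:** state the same all-cause collection window for the AE tables, and say that only related events are collected after it.

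The cost is a wording change, one call for each patient whose visit falls before Day 30, mainly early stoppers, and a few extra unrelated AEs, some of them arising after a new therapy has begun. No dose, schedule or treatment rule changes.

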## CONFIDENTIAL

- Female patients able to have children must have a human chorionic gonadotropin (HCG) pregnancy test (serum or urine test is acceptable).
- Radiological assessment of disease: This must be repeated at the end of the vaccination schedule. Tumour measurements must be documented according to Immune-Related Response Criteria (irRC). (Refer to [Section 10.0](#)). Thereafter, assessment of disease to be performed as per standard clinical practice.

### 7.4 Follow-up

#### 7.4.1 3, 6, 9 and 12 months post first vaccination

##### Patients should undergo the following assessments:

- Research blood samples 3, 6 and 12 months (all +/-1 week) post the first vaccination.
- At the above time points, an evaluation of any AST-VAC2 related AEs will also be performed. Assessments can be performed as clinically indicated.
- A further AE evaluation should be performed at 9 months post the first vaccination also. This can be in the form of a phone call to the patient.
- Any concomitant medications relevant to AST-VAC2-related AEs should be recorded.

All new and ongoing AST-VAC2-related AEs should be followed up until resolution or stabilisation, even if the patient goes onto another anti-cancer treatment. SAEs considered related to AST-VAC2 are always reportable regardless of the time elapsed.

#### 7.4.2 15, 18 and 21 month post first vaccination

Evaluation of any new or ongoing AST-VAC2-related AEs should be performed at 15, 18 and 21 months (i.e. quarterly). This can be in the form of a phone call to the patient. Any concomitant medications related to these AEs should also be recorded.

It is acceptable for there to be flexibility around when these quarterly visits take place but this should be checked with the Sponsor who will document the revised visit accordingly.

#### 7.4.3 Two years post first vaccination visit (survival follow up data collection).

All vaccinated patients should be followed up for OS, two years post the first vaccination. Evaluation of new or ongoing AST-VAC2-related AEs should be performed. Any concomitant medications relevant to these AEs should also be recorded. The AE information can be collected via a phone call to the patient. Survival information may be obtained from the patient's medical records.

For survival follow up, sites will be asked to provide the following information if known:

- Date of death or date of last contact if alive.
- Reason for death.
- All post trial anti-cancer treatment for primary disease.
- Date of radiological confirmed relapse(s), if post trial.
- WHO PS at time of relapse.
- Any other medically important information, in the opinion of the investigator.

No further patient trial related visits or assessments are required to collect this survival data. Survival follow up information may cease to be collected based on emerging data showing limited immune response and therefore limited benefit of continuing collection of long term follow up data. This will be discussed and agreed by the Sponsor and CI based on emerging data.

**7.4.4 Extended follow up (>2 years to 5 years post first vaccination)**

After the 2-year survival follow up has been completed, any patients who are still alive will continue to be followed up every three months by telephone until the end of the trial (unless the patient has died or withdrawn from the trial). If the patient has died, the date of death and cause of death will be recorded. Evaluation of new or ongoing AST-VAC2-related AEs should be performed. Any concomitant medications relevant to these AEs should also be recorded. It is acceptable for there to be flexibility around when these quarterly calls take place but this should be checked with the Sponsor who will document the revised visit accordingly.

**CONFIDENTIAL**

**7.5 Schedule of events**

Observation/Investigation	Pre-screening & trial screening	Within 7 days before study enrolment	During the trial			Two weeks post last vaccination	End of Vaccination visit 30 days after last vaccination	Research bloods: Up to 12 months post first vaccination g  Survival follow up: Up to 2 years post first vaccination f	Extended follow up: >2to 5 years post first vaccination (visits conducted by telephone)
			Vaccination at Weeks 1, 2, 3, 4, 5 and 6						
	Day -28 to -1 prior to first vaccination		Day -1 or Day of vaccination	Pre AST-VAC2 Within 15min prior	Post AST-VAC2 15 mins				
Written informed consent – HLA typing a	X								
Written informed consent– Main Trial b	X								
Adverse event evaluation l	From date of informed consent, throughout trial & monthly follow up thereafter until resolution j Ongoing drug-related AEs will be followed up until completion of extended follow up.								X n
Medical history	X								
Concomitant treatments	Throughout trial								X n
Radiological disease assessment k	X						X		
Pregnancy test (if applicable)		X					X		
Physical examination		X	X m				X		
Vital signs c		X		X	X		X		
WHO Performance Status d		X	X				X		
Demographics	X								
Height		X							
Weight		X					X		
Haematology, biochemistry, CEA		X	X e				X		
Urinalysis		X	X e				X		
Electrocardiogram		X					X		
AST-VAC2 administration	2 x id injections on each vaccination day, administered weekly, 7 days apart (+/- 1 day)								
Research bloods		X	Weeks 3, 4 and 6 pre-vaccination			X		3, 6 and 12 months post first vaccination	
Survival follow up l								X	

a) Patients will be asked to give written consent for HLA testing before any other further trial screening is performed. Thereafter, consent will be sought for the main trial.

## CONFIDENTIAL

It is acceptable that the HLA testing is performed outside of the 28 day window: important to note that this test will be performed by a central laboratory therefore sites should plan accordingly to ensure that following consent, the sample is taken and shipped to ensure timely reporting in preparation for the proposed first vaccination.

- b) HLA A\*02:01 positive patients will be asked consider consenting to the main trial for trial treatment and enter the screening period.
- c) Vitals to include temperature, seated BP, pulse rate.
- d) WHO PS to be assessed on day of vaccination as well as during screening.
- e) Haematology, biochemistry, CEA and urinalysis: Week 1 vaccination: laboratory tests must be repeated and reported prior to the first vaccination if the results used for enrolment purposes are >7 days prior to the day of vaccination. Thereafter laboratory parameters are to be measured on Day-1 or Day of vaccination. Haematology and biochemistry results do not need to be reported and checked before each vaccination is given.
- f) Follow up for overall survival to be captured for two years post the first vaccination.  
For extended follow up details, see [Section 12.0](#).
- g) Research blood sampling required, pre, during and post treatment – Please see [Section 8.0](#).  
[REDACTED]
- [REDACTED]
- j) Monthly follow-up required ONLY for those AEs and SAEs considered drug-related (highly probable, probable or possible) that are present at time that patient completes the End of Vaccination visit. Monthly follow-up to continue until resolution, to baseline, stabilisation or patient starts another anti-cancer treatment.  
AE evaluation also to be performed as per [Section 7.4](#).
- k) Radiological disease assessment prior to trial start may have been taken prior to informed consent as part of routine diagnostic procedures. Tumour measurements must be reported according to Immune Response Related Criteria (irRC).
- l) AE evaluation according to CTCAE v4.02 and protocol specific grading system for ISR.
- m) Symptom directed physical examination only.
- n) During extended follow up, new and ongoing AST-VAC2 related AEs should be reported and only concomitant medications relevant to these AST-VAC2 related AEs should be recorded.

## 8 PHARMACODYNAMIC ASSESSMENTS

### 8.1 Summary of Pharmacodynamic assessments

#### 1) Pre-screening assessment

	Biomarker	Technology	Source	Rationale	Time point	Patient group	Planned timing of analysis
1a	HLA A*02:01	Luminex or similar	Whole blood 3 mL *	Patient eligibility	Screening visit	All patients	Result required prior to further screening assessments

\* Analysis from the pre-screening HLA typing will report on several alleles. DNA extracted from the whole blood sample will be stored for further allele analysis as confirmed by the Sponsor, See 3h.

#### 2) Secondary Endpoints

	Biomarker	Technology	Source	Rationale	Time point	Patient group	Planned timing of analysis
2a	hTERT specific T cell ELISPOT analysis	ELISPOT	Whole blood  72 mL at baseline, thereafter, 48 mL to be taken at each time point	Identification of peptide specific T cells	
 
• Baseline
 
• Within one hour prior to 3rd, 4th and 6th vaccination
 
• 2 weeks (+/- 1 day) post last vaccination
 
• 3, 6, 12 months (+/- 1 week) post first vaccination
 
	All treated patients	Analysis as defined by the Sponsor.

